Appendix 2. Definition of Rescue Medications

The AD rescue therapy in this study is defined as: high-potency TCS and systemic AD therapy. The topical treatments and systemic treatments are defined as following:

1. Topical AD Treatment (including TCSs, TCI, and crisaborole)

Route of topical treatments includes: Topical and Transdermal.

TCS: ATC code is D07

High Potency TCS: ATC codes are D07AC or D07AD

Low or moderate potency TCS: ATC code is D07, excluding D07AC or D07AD

TCI: PT includes: TACROLIMUS, PIMECROLIMUS

Crisaborole: PT includes: CRISABOROLE

2. Systemic AD Treatment (including systemic corticosteroids, immunosuppressant, biologics, and phototherapy/PUVA)

Route of systemic treatments administration includes: Oral, Intra-Arterial, Intramuscular, Intraperitoneal, Intravenous, Subcutaneous, and Transdermal. (This condition applies to the following categories except for phototherapies.)

Systemic Corticosteroids: ATC code is H02

Immunosuppressant: Defined as: ATC2 is L04 or PTs of Abrocitinib or Ruxolitinib excluding PTs mentioned in Biologics

Biologics: Defined as following PTs:

Infliximab, Infliximabum, Etanercept, Etanerceptum, Adalimumab, Adalimumabum, Certolizumab, Certolizumabum, Certolizumab pegol, Golimumab, Golimumabum, Ozoralizumab, Afelimumab, Afelimumabum, Tumor Necrosis Factor Alpha (TNF-) Inhibitors, Tabalumab, Tregalizumab, Anakinra, Basiliximab, Basiliximabum, Daclizumab, Daclizumabum, Tocilizumab, Tocilizumabum, Mepolizumab, Mepolizumabum, Rilonacept, Rilonaceptum, Ustekinumab, Canakinumab, Briakinumab, Fezakinumab, Sirukumab, Sarilumab, Lebrikizumab, Secukinumab, Olokizumab, Gevokizumab, Brodalumab, Ladarixin, Ixekizumab, Dupilumab, Tildrakizumab, Tildrakizumabum, Reslizumab, Reslizumabum, Guselkumab, Guselkumabum, Olamkicept, Fletikumab, Bimekizumab, Mirikizumab, Risankizumab, Abatacept, Ligelizumab, Vedolizumab, Belimumab, Nemolizumab, Tralokinumab, Omalizumab

Phototherapy or PUVA:

Programming search of medication name (actual term or PT) contains 'photo' then medicals to manually review to confirm whether the medication in question is indeed 'Phototherapy' or 'Photochemotherapy'.

Appendix 3. Details of Combining Estimates and Test Statistics for Categorical Endpoints with Multiple Imputation

Following the implementation of MCMC-MI imputation as specified in Section 6.4.1, the 25 data sets with imputations should be set together and sorted by imputation number. The following sections describe the processes for combining inferences for the individual imputed data sets into 1 inference for reporting. All calculations are performed in SAS Software Version 9.4.

Summarize Unadjusted Response Rate

The response rates, overall and by treatment arm, and their associated SEs are computed for each imputed data set using PROC FREQ with the *riskdiff* option specified for the appropriate column in the TABLES statement. The response rates and SEs from the resulting output are combined across the 25 imputed data sets using PROC MIANALYZE, separately for each arm and the overall group.

Note that the estimate and 95% CI bounds output by PROC MIANALYZE are percentages (that is, they are in terms of the response rate). To obtain the number of responders, the estimated percentage is multiplied by the number of individuals in the analysis population and rounded to the nearest integer.

Compute Stratified Measures of Association

The common risk difference, common OR, and CMH test statistic are computed for each imputed data set using PROC FREQ with the *riskdiff* option for the appropriate column (for risk difference) and the *cmh* option (for OR and CMH test statistic) specified in the TABLES statement. Each of these analyses are stratified by geographic region, age group, and baseline disease severity via inclusion of these variables in the TABLES statement with the treatment and outcome variables.

Note that the PROC FREQ output corresponding to the Mantel-Haenszel method is used for the risk difference, and the output corresponding to the General Association statistic is used for the CMH statistic. PROC MIANALYZE is then called separately for each of these measures, with further details in the sections below.

Common Risk Difference

No transformation is necessary before using PROC MIANALYZE to combine the risk difference estimates and their associated SEs across the 25 imputed data sets. This procedure outputs an estimate of the common risk difference and the associated 95% CI bounds.

Common OR

The OR from each imputed data set is first transformed using the natural logarithm. The SE for each log OR (SE_{lOR}) is derived from the OR 95% CI bounds (LB_{OR} , UB_{OR}) according to the following equation: $SE_{lOR} = (\ln(UB_{OR}) - \ln(LB_{OR}))/ (2 * 1.96)$. The log OR and derived SE are then combined using PROC MIANALYZE, which outputs a combined estimate of the log OR and the associated 95% CI. Finally, these measures can be exponentiated to transform them back to the OR scale.

CMH Test

The CMH test statistic (CMH) from each imputed data set is transformed using the Wilson-Hilferty transformation and standardized so that it has approximately a standard normal distribution (Ratitch et al. 2013). In particular, the transformed CMH statistic is computed as

$$CMH_{WH} = \left(\frac{CMH}{df} \right)^{\frac{1}{3}} - \frac{1 - \frac{2}{9*df}}{\sqrt{\frac{2}{9*df}}},$$

where df is the degrees of freedom of the CMH statistic. Then the SE for each CMH_{WH} is 1, and PROC MIANALYZE is used to output a combined estimate of the transformed CMH statistic. Note that the 2-sided p-value output by PROC MIANALYZE is not used directly, but instead the 1-sided p-value is computed manually using both the t statistic and 2-sided p-value output by PROC MIANALYZE; if t statistic is >0 , then the 1-sided p-value is computed as one half of the 2-sided p-value; otherwise, the 1-sided p-value is computed as one half of the 2-sided p-value. The resulting 1-sided p-value is reported as the pooled p-value for the CMH test.

Signature Page for VV-CLIN-075212 v1.0

Approval	PPD Statistician 05-Dec-2022 00:22:51 GMT+0000
----------	--

Signature Page for VV-CLIN-075212 v1.0

Approved on 05 Dec 2022 GMT

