6.5.1. Permitted and Prohibited Treatments and Procedures

Permitted medications

The use of concomitant medications for other medical conditions (e.g., hypertension, diabetes, acute infections) is permitted during this study. Inhaled corticosteroids and bronchodilators to control asthma are permitted.

In addition, TCS or TCI may be used during the study (low- or mid-potency only).

Participants may use TCS (described below) for AD symptoms starting at the baseline visit (randomization: Visit 2/Day 1).

Participants may taper or stop TCS use, as needed. If AD lesions return or a participant experiences a flare, TCS treatment may be resumed at the participant's discretion.

Low-potency TCS or TCIs may be used for sensitive areas only (i.e., face, neck, intertriginous, and genital areas).

Participants may use the following TCS, if needed:

- a mid-potency TCS: triamcinolone acetonide cream 0.1%, and
- a low-potency TCS: hydrocortisone 1% cream (for use on sensitive skin areas, e.g., face).

All TCS use should be recorded in the eCRF.

Prohibited medications and procedures

The introduction of medications or therapies for other medical conditions known to affect AD (e.g., systemic corticosteroids, mycophenolate-mofetil, IFN- γ , Janus kinase inhibitors, cyclosporine, azathioprine, methotrexate, phototherapy or photochemotherapy, or phosphodiesterase-4 inhibitors such as crisaborole) are not permitted during the study.

The use of systemic corticosteroids for the treatment of AD is prohibited and requires permanent discontinuation of study drug (Section 7.1.2). If used for treatment of AEs (for example, worsening of existing condition, such as asthma exacerbation), it will be treated as rescue medication as per the Section 6.5.3.

Acute severe infections can be treated with systemic antibiotics, use of which must be recorded in the eCRF. However, chronic treatment with systemic antibiotics is not permitted.

The use of a tanning booth/parlor is not permitted during the trial.

Cannabinoid treatments for AD are prohibited.

Planned or anticipated major medical procedures or surgeries should be avoided during the trial.

See Section 6.5.3 for details on approved rescue medications and timing of use.

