9.4.3.1. Missing Data

The method of handling missing efficacy data will be as follows for endpoints:

Percentage of participants at Week 16 achieving:

- an IGA score of 0 or 1 and a reduction of ≥ 2 points from baseline
- $\geq 75\%$ reduction from baseline in EASI score (EASI-75)
- $\geq 90\%$ reduction from baseline in EASI score (EASI-90)
- ≥ 4 -point improvement from baseline in Pruritus NRS score in participants with baseline score of ≥ 4

For participants who receive systemic rescue treatment or withdraw from the study due to lack of efficacy, values should be set to the participant's baseline value subsequent to this time through Week 16. The Markov Chain Monte Carlo (MCMC) multiple imputation will be used to handle the remaining missing data. Imputation will be conducted within each treatment group independently so the pattern of missing observations in one treatment group cannot influence the missing value imputation in the other treatment group. For each imputation process, 25 datasets with imputations will be calculated. Each complete data set will be analyzed with the specified analysis. The results from these analyses will be combined into a single inference using SAS PROC MIANALYZE.

For binary responses related to EASI and IGA, the binary response variables will be calculated based on the multiply imputed datasets that have been created. Because the MCMC algorithm is

based on the multivariate normal model, imputed values for IGA will not generally be one of the discrete values used in IGA scoring (0, 1, 2, 3, or 4). Therefore, to derive the binary IGA response variable, standard rounding rules will be applied to the imputed values. For example, if a participant has an IGA score imputed as 1.4 (and assuming a baseline IGA score of 3), the imputed value would be rounded down to 1, and the minimum change from baseline of 2 would have been met. This participant would be considered a responder. For derivation of an EASI-75 and EASI-90 responses, no rounding will be performed.

The imputed Week 16 EASI value will be compared directly to the observed baseline EASI value to determine whether a reduction of at least 75% was achieved for EASI-75. The imputed Week 16 EASI value will be compared directly to the observed baseline EASI value to determine whether a reduction of at least 90% was achieved for EASI-90. Imputation of continuous data will be analogous to that of binary variables; details will be provided in the SAP.

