6.2. Primary and Supportive Estimands

There will be 1 estimand of interest in analyzing the primary endpoint and 3 estimands of interest in analyzing secondary endpoints for the double-blinded treatment period. For secondary endpoints, 2 types of intercurrent events (ICEs) in terms of estimating the treatment effects for the treatment period will be considered: initiation of rescue medication as defined in Appendix 2 and permanent treatment discontinuation.

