6.2.2. Secondary and Supportive Estimands for Secondary Endpoints

The secondary estimand for secondary endpoints is a hybrid estimand representing the secondary clinical question of interest: what is the difference between treatment conditions (that is lebrikizumab vs placebo), in the target participant population, of successful response rates or means achieved after 16 weeks, without use of rescue medication, and if all participants continued with treatment except those who discontinued due to lack of efficacy?

The **secondary estimand for secondary endpoints** is described by the following attributes:

- Population: Defined through appropriate inclusion/exclusion (I/E) criteria to reflect the targeted patient population for approval
- Endpoint: Apply to all secondary endpoints
- How to account for ICEs:
 - Subjects who used rescue medication or discontinued treatment because of lack of efficacy prior to Week 16 will be considered as treatment failures, that is, nonresponder, after the ICEs. Therefore, composite strategy is used for these types of ICEs
 - For subjects who discontinued treatment because of reasons other than lack of efficacy prior to Week 16, a hypothetical strategy will be used to estimate what the treatment effect would have been if subjects continued with treatment. Therefore, hypothetical strategy is used for these types of ICEs
- Population-level summary: Difference in response proportions or means between treatment conditions

The **supportive estimand for categorical secondary endpoints** is a composite estimand as described by the following attributes:

- Population: Defined through appropriate I/E criteria to reflect the targeted patient population for approval
- Endpoint: Apply to all category secondary endpoints
- How to account for ICEs:
 - Subjects who used rescue medication or discontinued treatment prior to Week 16 will be considered as treatment failures, that is, nonresponder, after the ICEs. Therefore, composite strategy is used for these types of ICEs
- Population-level summary: Difference in response proportions between treatment conditions

The **supportive estimand for continuous secondary endpoints** is a hypothetical estimand as described by the following attributes:

- Population: Defined through appropriate I/E criteria to reflect the targeted patient population for approval
- Endpoint: Apply to all continuous secondary endpoints
- How to account for ICEs:

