6.4.1. Markov Chain Monte Carlo Multiple Imputation

The method of handling missing efficacy data as mentioned in [Table KGAK.6.4](#) will be as follows for both binary and continuous endpoints.

For participants who receive rescue medication (high-potency topical corticosteroids [TCS] or systemic AD treatment, defined in [Appendix 2](#)) or discontinue from the study treatment due to lack of efficacy, values should be set to the participant's baseline value subsequent to this time through Week 16. The Markov chain Monte Carlo multiple imputation (MCMC-MI) will be used to handle the remaining missing data. Imputation will be conducted within each treatment group independently so the pattern of missing observations in 1 treatment group cannot influence

missing value imputation in another. The SAS PROC MI with the MCMC option will be used to conduct the MCMC-MI. The imputation model will include the relevant baseline and postbaseline.

For each imputation process, 25 datasets with imputations will be calculated. The initial seed values are given in [Table KGAK.6.5](#). Each complete data set will be analyzed with the specified analysis. The results from these analyses will be combined into a single inference using SAS PROC MIANALYZE.

For binary responses related to the Eczema Area and Severity Index (EASI) and IGA, the binary response variables will be calculated based on the multiply imputed datasets that have been created. Because the MCMC algorithm is based on the multivariate normal model, imputed values for IGA will not generally be one of the discrete values used in IGA scoring (0, 1, 2, 3, or 4). Therefore, to derive the binary IGA response variable, standard rounding rules will be applied to the imputed values. For example, if a participant has an IGA score imputed as 1.4 (and assuming a baseline IGA score of 3), the imputed value would be rounded down to 1, and the minimum change from baseline of 2 would have been met. This participant would be considered a responder.

For derivation of a $\geq 75\%$ reduction from baseline in EASI score (EASI 75) and $\geq 90\%$ reduction from baseline in EASI score (EASI 90) response, no rounding will be performed. The imputed Week 16 EASI value will be compared directly to the observed baseline EASI value to determine whether a reduction of at least 75% or 90% was achieved.

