6.4.2. Mixed-Model for Repeated Measures

Mixed-model for repeated measures analyses will be performed on continuous endpoints to mitigate the impact of missing data. This approach assumes missing observations are missing at random (missingness is related to observed data) and borrows information from participants in the same treatment arm taking into account both the missingness of data through the correlation of the repeated measurements.

The values subsequent to rescue medication use (high-potency TCS or systemic AD treatment, defined in [Appendix 2](#)) or treatment discontinuation will be made missing before applying the MMRM. The MMRM is described in Section [6.1.2](#).

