6.4.4. Nonresponder Imputation

The nonresponder imputation (NRI) method will be used to handle missing data relative to the supportive estimand for categorical endpoints (composite). Participants who receive rescue medication (high potency TCS or systemic AD treatment, defined in [Appendix 2](#)), or discontinue treatment, will be set to nonresponse subsequent to this time through Week 16. Intermittent missing values will also be set to nonresponse.

The NRI method imputes missing values as nonresponders and can be justified based on the composite strategy (ICH E9R1) for handling ICEs. In this strategy, participants are defined as

responders only if they meet the clinical requirements for response at the predefined time AND they remain on the assigned study treatment (i.e., not using rescue medications and not having missing values due to other reasons). Failing either criteria by definition makes them nonresponders.

Randomized participants without at least 1 postbaseline observation will also be defined as nonresponders for all visits for the NRI analysis.

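### Crisaborole is not counted as rescue in SAP Appendix 2, so mITT secondary efficacy values after its use are analysed as rescue-free when the participant stays on study drug

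*SAP*

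**What the plan says.** **SAP.**

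- Section 6.2 recognises two intercurrent events for the secondary endpoints: "initiation of rescue medication as defined in Appendix 2 and permanent treatment discontinuation".
- Appendix 2 defines rescue: "The AD rescue therapy in this study is defined as: high-potency TCS and systemic AD therapy". It identifies high-potency TCS by ATC codes D07AC and D07AD. It gives crisaborole its own preferred term among topical AD treatments, and crisaborole is not on the systemic list.
- Section 6.2.2 asks about "successful response rates or means achieved after 16 weeks, without use of rescue medication".
- Section 6.4.1 (multiple imputation) resets values to baseline: "For participants who receive rescue medication (high-potency topical corticosteroids [TCS] or systemic AD treatment, defined in" Appendix 2. It does the same after treatment discontinuation for lack of efficacy.
- Section 6.4.2 (MMRM) sets to missing "The values subsequent to rescue medication use (high-potency TCS or systemic AD treatment, defined in" Appendix 2, and also values after treatment discontinuation. Section 6.4.3 (LOCF) uses the same trigger.
- Section 6.4.4 (NRI) requires a responder to be "not using rescue medications and not having missing values due to other reasons", with the same two rescue classes.
- Section 6.9 tabulates crisaborole within topical AD treatment by arm, for mITT and PPS. It defines flare through rescue therapy and points to Appendix 2 for the definition of rescue.

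**Protocol.**

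- Section 6.5.1 sets the permitted background: "In addition, TCS or TCI may be used during the study (low- or mid-potency only". Its prohibited list names crisaborole.
- Section 6.5.3 opens rescue to any locally approved AD treatment, at the investigator's discretion.
- Section 9.4.3.1 has a narrower reset rule: "For participants who receive systemic rescue treatment or withdraw from the study due to lack of efficacy".

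**The concern.** The secondary estimand is meant to describe outcomes achieved without rescue. Low- and mid-potency TCS and TCI are also outside the rescue definition, but the protocol permits them as background, so leaving them out is coherent. Crisaborole is different. Exclusion criterion [30] washes it out alongside TCS and calcineurin inhibitors, yet Protocol 6.5.1 re-admits only TCS and TCI. It is therefore neither permitted background nor coded rescue. A good Week 16 score obtained with its help would be credited to the randomised arm.

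The same definition drives the percentage rescued by visit, the time to first rescue and the flare summary, so crisaborole given as rescue would be missing from those too. At stake is the reading of secondary and exploratory efficacy results, for which SAP 6.1.2 plans CMH p-values and 95% CIs.

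**Working it through.** **1. The plan's own design figure (context only).** Inputs from Protocol 9.2: 109 per arm, two-sided 90% Wald CI. Half-width = 1.645 × √(2p(1−p)/109). At p = 0.83 this is 0.0837 (stated 0.08). At p = 0.90 it is 0.0668 (stated 0.07). Both reproduce. They concern the vaccine endpoints, which do not use the rescue rule.

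**2. Rule trace for a participant who uses crisaborole and stays on study drug.**

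| Rule | Trigger | Met? |
|---|---|---|
| SAP 6.2 | Appendix 2 rescue, or permanent treatment discontinuation | No |
| SAP 6.4.1 | High-potency TCS, systemic AD treatment, or treatment stopped for lack of efficacy | No |
| SAP 6.4.2, 6.4.3, 6.4.4 | Same two rescue classes, or treatment stopped | No |
| mITT (SAP 6.1.1) | Excludes two sites only | Stays in |
| Protocol 7.1.2 mandatory stop for rescue | Systemic corticosteroid, immunosuppressant or phototherapy | No |

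Later IGA, EASI, NRS, Sleep-loss and BSA values are therefore analysed as observed.

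**3. Size for a responder endpoint.** The documents give no crisaborole use, so every input here is an assumption: 120 per arm (240 randomised 1:1, before the two sites are dropped), and a fraction r = 0.20 to 0.50 of users counted as responders. Resetting these users to nonresponse changes the difference (lebrikizumab minus placebo) by 100 × net users × r / n, where net users = placebo minus lebrikizumab and r is the same in both arms.

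| Net placebo users | n | Change, points |
|---|---|---|
| 1 (0.8% of arm) | 120 | 0.2 to 0.4 |
| 3 (2.5%) | 120 | 0.5 to 1.3 |
| 6 (5.0%) | 120 | 1.0 to 2.5 |
| 6 | 109 | 1.1 to 2.8 |

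The sign reverses if the excess is on lebrikizumab: 6 net users give −1.0 to −2.5. Counting affected responders directly, 0 to 10 on placebo and 0 to 5 on lebrikizumab give a range from 100 × (0−5)/120 = −4.2 to 100 × (10−0)/120 = +8.3 points.

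Equal use with equal response gives zero. Equal use with unequal response does not: 6 users per arm, with r = 0.50 on lebrikizumab and 0.20 on placebo, give 100 × 6 × (0.20−0.50)/120 = −1.5.

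**4. Scale against sampling error.** 95% half-width = 1.96 × √(p1(1−p1)/120 + p2(1−p2)/120). At an assumed 40% vs 20% this is 11.3 points. At 30% vs 10% it is 9.8, and at 50% vs 25% it is 11.8. One affected responder is worth 100/120 = 0.83 points. Moving the difference by half the half-width needs:

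- 40% vs 20%: 5.66/0.833, rounded up to 7 net affected responders, or 7/0.50 = 14 to 7/0.20 = 35 net users (12% to 29% of an arm)
- across the other two cases: 6 to 8 net affected responders, or 6/0.50 = 12 to 8/0.20 = 40 net users (10% to 33% of an arm)

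**5. Continuous endpoints.** Under reset to baseline, the unadjusted arm mean moves by users × their mean change / n. Nothing in the documents allows a figure to be put in.

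**The case against.** The strongest reply is that the SAP is internally consistent. Rescue is a defined term, 6.2 points to the definition, and all four methods apply it alike. The SAP is also already wider than Protocol 9.4.3.1, because it adds high-potency TCS. This stands: a reader might infer that the SAP dropped a protocol rule on crisaborole, and there was none. What remains is that the definition is narrower than the rescue Protocol 6.5.3 allows, and it leaves an agent listed as not permitted in the same position as permitted background.

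Second, few participants may be affected. Crisaborole is not among the 6.5.3 examples, which favour more intense treatment. Protocol 7.2 describes leaving the study before another effective agent is introduced. That will remove some users, but it sits under reasons a participant may withdraw, so it does not guarantee removal. A reader might also take all crisaborole use to be a violation. The text does not go that far, because the 6.5.1 sentence is framed around therapies for other conditions, and 6.5.3 could admit crisaborole as rescue if it is locally approved.

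Third, the PPS offers some protection. Its listed criterion names systemic rescue, but SAP 6.1.1 makes the list open-ended and sends further deviations to a tracker, and SAP 6.15 gives interfering concomitant medication as an example of an important deviation. Some users may well be excluded this way, although the deciding plan is a separate document. None of this changes the mITT results. Table KGAK.6.7 repeats IGA 0/1, EASI 75, EASI 90 and EASI change in the PPS, but not Pruritus NRS, Sleep-loss or BSA.

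Fourth, Protocol 6.5.1 also prohibits cannabinoid treatments for AD, and Appendix 2 does not list them. That is correct, and the fix below leaves it open. Crisaborole is singled out because it is already coded.

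**Conclusion.** The gap is real but minor. In mITT, secondary efficacy values after crisaborole use are analysed as rescue-free when the participant stays on study drug, and the percentage-rescued, time-to-first-rescue and flare summaries omit that use.

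The size cannot be determined from the documents and is probably small. Under the assumptions above, a net 1 to 6 users in one arm is worth 0.2 to 2.5 points, and a shift of half a CI half-width needs net use in 10% to 33% of an arm. mITT arms will be below 120 if the two excluded sites enrolled anyone, by a number not given.

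Two stronger readings are tempting. One is that the bias must be conservative. That holds only if more affected responders are on placebo. An excess on lebrikizumab would favour lebrikizumab, and the documents give no use by arm. The other is that the main conclusions are at risk. The co-primary vaccine endpoints are analysed in the PPS without this rescue rule, and Protocol 9.1 calls the study descriptive. This is a low-priority improvement.

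**What to change.** Keep Appendix 2 and the main analysis as planned. First give crisaborole its own row in the by-arm AD treatment table of SAP 6.9. If it shows any use on or after Day 1, add one mITT sensitivity analysis of the secondary efficacy endpoints and the rescue-use summaries, with preferred term CRISABOROLE counted as rescue. Later values would then go to baseline under multiple imputation, to missing under MMRM and LOCF, and to nonresponse under NRI. If there are no users, say so and skip the rerun.

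Label the analysis as added after the Week 16 unblinding, since SAP Version 3 itself was approved after that lock.

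The cost is one extra term in one flag and one rerun of the tables. The term is already in Appendix 2, and Protocol 6.5 already collects start date, indication and reason for use. The downside is one more post-unblinding analysis, with possibly a few more participants set to nonresponse in it.
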